11.10.7. Safety Figures

Not applicable.

11.10.8. Pharmacokinetic Tables

Pharmacokinetic : Tables					
No.	Population	IDSL / TST ID / Example Shell	Title	Programming Notes	Deliverable [Priority]
Pharmacokinetics					
4.1.	PK	PKCT1	Summary of Serum GSK2646264 Pharmacokinetic Concentrations versus time by actual dose		IA[1],SAC [1]
4.2.	PK	PKPT1	Summary of Derived Serum GSK2646264 Pharmacokinetic Parameters by actual dose		IA[1],SAC [1]
4.3.	PK	PKPT3	Summary of Log-Transformed Derived Serum GSK2646264 Pharmacokinetic Parameters by actual dose		IA[1],SAC [1]

11.10.9. Pharmacokinetic Figures

Pharmacokinetic : Figures					
No.	Population	IDSL / TST ID / Example Shell	Title	Programming Notes	Deliverable [Priority]
Pharmacokinetics					
4.1.	PK	PKCF1	Individual Serum GSK2646264 Concentration-Time Plot (Linear and Semi-log)	1. x-axis should display Actual relative time 2. Include line for LLQ along with footnote defining LLQ value. 3. Include values below LLQ	IA[1],SAC [1]
4.2.	PK	PKCF3	Median Serum GSK2646264 Concentration-Time Plot (Linear and Semi-log)	1. X-axis should display Planned relative time 2. Include line for LLQ along with footnote defining LLQ value. 3. Include values below LLQ Use different symbols for treatments	IA[1],SAC [1]
4.3.	PK	PKCF4	Mean and SD of Serum GSK2646264 Concentration-Time Plot (Liner and Semi-log)	1. X-axis should display Planned relative time 2. Include line for LLQ along with footnote defining LLQ value. 3. Include values below LLQ Use different symbols for treatments	IA[1],SAC [1]

11.10.10. Pharmacodynamic and Biomarker Tables

Pharmacodynamic and Biomarker: Tables					
No.	Population	IDSL / TST ID / Example Shell	Title	Programming Notes	Deliverable [Priority]
Pharmacodynamics					
5.1.	PD	Non-Standard_PDT 1	Allergen Challenge, Weal Area - Summary Statistics (Absolute and Percent of Inhibition)	Absolute and Percent of Inhibition Part A + B	IA[1],SAC [1]
5.2.	PD	Example Non-Standard_PDT 1 modified based on endpoint.	Allergen Challenge, Weal Volume – Summary Statistics (Absolute and Percent of Inhibition)	Absolute and Percent of Inhibition Part A + B	IA[1],SAC [1]
5.3.	PD	Example Non-Standard_PDT 1 modified based on endpoint.	Allergen Challenge, Longest Weal Diameter- Summary Statistics (Absolute and Percent of Inhibition)	Absolute and Percent of Inhibition Part A + B	IA[1],SAC [1]
5.4.	PD	Example Non-Standard_PDT 1 modified based on endpoint.	Allergen Challenge, Weal perpendicular length - Summary Statistics (Absolute and Percent of Inhibition)	Absolute and Percent of Inhibition Part A + B	IA[1],SAC [1]
5.5.	PD	Example Non-Standard_PDT 1 modified based on endpoint.	Allergen Challenge, Flare Erythema - Summary Statistics (Absolute and Percent of Inhibition)	Absolute and Percent of Inhibition Part A + B	IA[1],SAC [1]

Pharmacodynamic and Biomarker: Tables					
No.	Population	IDSL / TST ID / Example Shell	Title	Programming Notes	Deliverable [Priority]
5.6.	PD	Example Non-Standard_PDT 1 modified based on endpoint.	Cold Temp Test, Change in critical temperature thresholds	Absolute Part B only	SAC [1]
5.7.	PD	Example Non-Standard_PDT 1 modified based on endpoint.	UAS7 Scores – Summary Statistics (Absolute and Change from Baseline)	Absolute and Change from Baseline Part C only	SAC [1]
5.8.	PD	Example Non-Standard_PDT 2	Change from baseline in composite total UAS7 Scores – Treatment Comparison	Paired t-Test (95%CI) and ANCOVA to compare treatments groups. Pre-Dose Value as Covariate Part C only	SAC [1]
5.9.	PD	Example Non-Standard_PDT 1 modified based on endpoint.	UAS7 Components – Summary Statistics (Absolute and Change from Baseline)	Absolute and Change from Baseline Part C only	SAC [1]
5.10.	PD	Example Non-Standard_PDT 2 modified based on endpoint.	Change from baseline in composite total UAS7 Components – Treatment Comparison	Paired t-Test (95%CI) and ANCOVA to compare treatments groups. Pre-Dose Value as Covariate Part C only	SAC [1]

Pharmacodynamic and Biomarker: Tables					
No.	Population	IDSL / TST ID / Example Shell	Title	Programming Notes	Deliverable [Priority]
5.11.	PD	Example Non-Standard_PDT 1 modified based on endpoint.	Angioedema Activity Score (AAS) – Summary Statistics (Absolute and Change from Baseline)	Absolute and Change from Baseline Part C only	SAC [1]
5.12.	PD	Example Non-Standard_PDT 2 modified based on endpoint.	Change from baseline in total Angioedema Activity Score (AAS) – Treatment Comparison	Paired t-Test (95%CI) and ANCOVA to compare treatments groups. Pre-Dose Value as Covariate Part C only	SAC [1]
5.13.	PD	Example Non-Standard_PDT 1 modified based on endpoint.	Dermatology Life Quality Index (DLQI) – Summary Statistics (Absolute and Change from Baseline)	Absolute and Change from Baseline Part C only Sum-Score and Analysis of Subscores	SAC [1]
5.14.	PD	Example Non-Standard_PDT 2 modified based on endpoint.	Change from baseline in total Dermatology Life Quality Index (DLQI) – Comparison Improvement from baseline	Paired t-Test (95%CI) Part C only No treatment comparison involved. Improvement from baseline in Quality Index	SAC [1]

Pharmacodynamic and Biomarker: Tables					
No.	Population	IDSL / TST ID / Example Shell	Title	Programming Notes	Deliverable [Priority]
Biomarker					
5.15.	PD	Example Non-Standard_PDT 1 modified based on endpoint.	Inhibition of CD69 biomarker by strength, BSA and day – Summary Statistics	Part A + C	IA[1],SAC [2]
5.16.	PD	Example Non-Standard_PDT 1 modified based on endpoint.	Relationship between Basophil Histamine (BHR) test and Weal Characteristics	Part C only No treatment comparison involved.	SAC[2]

11.10.11. Pharmacodynamic Figures

Pharmacodynamic : Figures					
No.	Population	IDSL / TST ID / Example Shell	Title	Programming Notes	Deliverable [Priority]
Pharmacodynamics					
5.1.	PD	Non-Standard _PD_F1	Allergen Challenge, Weal Area (Percent of Inhibition) - Individual Subject Plot	Part A + B Page by : Treatment X-Axis : Continuous scale for visit (days) Y-Axis : Scaled accordingly to Parameter and include parameter name Legend : Subject	SAC [1]
5.2.	PD	Non-Standard _PD_F2	Allergen Challenge, Weal Area (Percent of Inhibition, absolute value) - Box Plot	Part A + B X-Axis : Days Y-Axis : Result Legend : Treatment	SAC [1]

Pharmacodynamic : Figures					
No.	Population	IDSL / TST ID / Example Shell	Title	Programming Notes	Deliverable [Priority]
5.3.	PD	Example Non-Standard _PD_F1	Allergen Challenge, Weal Volume (Percent of Inhibition) - Individual Subject Plot	Part A + B Page by : Treatment X-Axis : Continuous scale for visit (days) Y-Axis : Scaled accordingly to Parameter and include parameter name Legend : Subject	SAC [1]

Pharmacodynamic : Figures					
No.	Population	IDSL / TST ID / Example Shell	Title	Programming Notes	Deliverable [Priority]
5.4.	PD	Example Non-Standard _PD_F2	Allergen Challenge, Weal Volume (Percent of Inhibition, absolute value) - Box Plot	Part A + B X-Axis : Days Y-Axis : Result Legend : Treatment	SAC [1]
5.5.	PD	Example Non-Standard _PD_F1	Allergen Challenge, longest weal Diameter (Percent of Inhibition) - Individual Subject Plot	Part A + B Page by : Treatment X-Axis : Continuous scale for visit (days) Y-Axis : Scaled accordingly to Parameter and include parameter name Legend : Subject	IA[1],SAC [1]
5.6.	PD	Example Non-Standard _PD_F2	Allergen Challenge, longest Weal Diameter (Percent of Inhibition, absolute value) - Box Plot	Part A + B X-Axis : Days Y-Axis : Result Legend : Treatment	IA[1],SAC [1]

Pharmacodynamic : Figures					
No.	Population	IDSL / TST ID / Example Shell	Title	Programming Notes	Deliverable [Priority]
5.7.	PD	Example Non-Standard _PD_F1	Allergen Challenge, Weal perpendicular length (Percent of Inhibition) - Individual Subject Plot	Part A + B Page by : Treatment X-Axis : Continuous scale for visit (days) Y-Axis : Scaled accordingly to Parameter and include parameter name Legend : Subject	IA[1],SAC [1]
5.8.	PD	Example Non-Standard _PD_F2	Allergen Challenge, Weal perpendicular length (Percent of Inhibition, absolute value) - Box Plot	Part A + B X-Axis : Days Y-Axis : Result Legend : Treatment	IA[1],SAC [1]
5.9.	PD	Example Non-Standard _PD_F1	Allergen Challenge, Flare Erythema (Percent of Inhibition) - Individual Subject Plot	Part A + B Page by : Treatment X-Axis : Continuous scale for visit (days) Y-Axis : Scaled accordingly to Parameter and include parameter name Legend : Subject	IA[1],SAC [1]

Pharmacodynamic : Figures					
No.	Population	IDSL / TST ID / Example Shell	Title	Programming Notes	Deliverable [Priority]
5.10.	PD	Example Non-Standard _PD_F2	Allergen Challenge, Flare Erythema (Percent of Inhibition, absolute value) - Box Plot	Part A + B X-Axis : Days Y-Axis : Result Legend : Treatment	IA[1],SAC [1]
5.11.	PD	Example Non-Standard _PD_F1	Cold Temp Test (Change) - Individual Subject Plot	Part B only Page by : Treatment X-Axis : Continuous scale for visit (days) Y-Axis : Scaled accordingly to Parameter and include parameter name Legend : Subject	SAC [1]
5.12.	PD	Example Non-Standard _PD_F2	Cold Temp Test (Change) - Mean (95% CI) Plot	Part B only X-Axis : Days Y-Axis : Mean (\pm 95% CI) Result Legend : Treatment	SAC [1]
5.13.	PD	Example Non-Standard _PD_F2	UAS7 Score (Change from Baseline) - Mean (95% CI) Plot	Part C only X-Axis : Days Y-Axis : Mean (\pm 95% CI) Result Legend : Treatment	,SAC [1]

Pharmacodynamic : Figures					
No.	Population	IDSL / TST ID / Example Shell	Title	Programming Notes	Deliverable [Priority]
5.14.	PD	Example Non-Standard _PD_F2	Angiodema Activity ScoreScore (AAS) (Change from Baseline) - Mean (95% CI) Plot	Part C only X-Axis : Days Y-Axis : Mean (\pm 95% CI) Result Legend : Treatment	SAC [1]
5.15.	PD	Example Non-Standard _PD_F2	Dermatology Life Quality Index (DLQI) - Box Plot	Part C only X-Axis : Days Y-Axis : Result Legend : Treatment	SAC [1]

11.10.12. ICH Listings

ICH : Listings					
No.	Population	IDSL / TST ID / Example Shell	Title	Programming Notes	Deliverable [Priority]
Randomisation					
1.	Safety	CP_TA1	Listing of Randomised and Actual Treatments		IA [1], SAC [1]
Subject Disposition					
2.	Safety	ES7	Listing of Reasons for Screen Failure		IA [1], SAC [1]
3.	Safety	ES2	Listing of Reasons for Withdrawal		IA [1], SAC [1]
4.	Safety	DV2	Listing of Important Protocol Deviations		IA (SAC)
5.	Safety	ES2	Listing of Exclusions from Per Protocol Population		IA (SAC)
Inclusion and Exclusion Criteria					
6.	Safety	IE3	Listing of Subjects with Inclusion/Exclusion Criteria Deviations		IA [1], SAC [1]
Demographics					
7.	Safety	DM2	Listing of Demographic Characteristics		IA [1], SAC [1]
8.	Safety	DM9	Listing of Race		IA [1], SAC [1]
Medical History					
9.	Safety	MH2	Listing of Medical History		IA [1], SAC [1]
Concomitant Medication					
10.	Safety	CP_CM3	Listing of Concomitant Medication by Generic Term		IA [1], SAC [1]
Study Drug Exposure					
11.	Safety	EX3	Listing of Exposure Data	If applicable adapt to study data	IA [1], SAC [1]

ICH : Listings					
No.	Population	IDSL / TST ID / Example Shell	Title	Programming Notes	Deliverable [Priority]
Adverse Events					
12.	Safety	AE7	Listing of All Adverse Events		IA [1], SAC [1]
13.	Safety	CP_AE8	Listing of Subject Numbers for Individual Adverse Events		IA [1], SAC [1]
14.	Safety	CP_AE8a	Listing of Serious Adverse Events		IA [1], SAC [1]
15.	Safety	CP_AE8	Listing of Adverse Events Leading to Withdrawal from Study		IA [1], SAC [1]
Clinical Laboratory Assessments					
16.	Safety	CP_LB5	Listing of Haematology Abnormalities of Potential Clinical Importance		IA [1], SAC [1]
17.	Safety	CP_LB5	Listing of All Haematology Laboratory Data for Subjects with Abnormalities of Potential Clinical Importance	Including change from Baseline	IA [1], SAC [1]
18.	Safety	CP_LB5	Listing of Clinical Chemistry Abnormalities of Potential Clinical Importance		IA [1], SAC [1]
19.	Safety	CP_LB5	Listing of Clinical Chemistry Laboratory Data for Subjects with Abnormalities of Potential Clinical Importance	Including change from Baseline	IA [1], SAC [1]
20.	Safety	CP_LB5	Listing of All Hematology Laboratory Data for Subjects with Adverse Events of Interest		IA [1], SAC [1]
21.	Safety	UR2b	Listing of Urinalysis Data for Subjects with Abnormalities of Potential Clinical Concern		IA [1], SAC [1]
Electrocardiogram (ECG)					
22.	Safety	CP_EG3	Listing of ECG Values of Potential Clinical Importance		IA [1], SAC [1]

CONFIDENTIAL

200196

ICH : Listings					
No.	Population	IDSL / TST ID / Example Shell	Title	Programming Notes	Deliverable [Priority]
23.	Safety	CP_EG3	Listing of All ECG Values for Subjects with a Value of Potential Clinical Importance	Including change from Baseline	IA [1], SAC [1]
24.	Safety	CP_EG5	Listing of Abnormal ECG Findings		IA [1], SAC [1]
Vital Signs					
25.	Safety	CP_VS4	Listing of Vital Signs of Potential Clinical Importance		IA [1], SAC [1]
26.	Safety	CP_EG3	Listing of All Vital Sign for Subjects with a Value of Potential Clinical Importance	Including change from Baseline	IA [1], SAC [1]
27.	Safety	CP_VS4	Listing of All Vital Signs for Subjects with Values of Potential Clinical Importance		IA [1], SAC [1]

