**Table 6 Summary of Key Issues, Their Impact and Strategy to Mitigate Risk**

Potential risk	Summary of data	Impact- eligibility criteria	Strategy-monitoring/stopping criteria
Hypersensitivity	
There may be potential for hypersensitivity reactions from the procedures used in the study or if subjects are allergic to ingredients in the study medications.
 
There is no previous experience of GSK2646264 or of the matched placebo in humans
	
Subjects will be asked at screening if they are allergic to any of the ingredients – if known,
 
Subjects will be excluded from the study if they are allergic to any ingredient of the study medications or if they have previously experienced an anaphylactic reaction.
	
Subjects will undergo regular medical assessment and instructed what action to take in the event of experiencing an allergic reaction.

Skin prick	
There have been rare reports of systemic allergic reactions following skin prick testing (Heinzerling, 2013)
	
Subjects will be excluded from the study if have previously experienced an anaphylactic reaction.
 
Subjects will be excluded from the study if the subject has a reaction which contraindicates to the study
	
Skin prick testing will be performed in a facility with appropriate emergency equipment available in case of the need for treatment for systemic allergic reaction.

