### **4.4. Screen and Baseline Failures**

Screen failures are defined as subjects who consent to participate in the clinical trial but are never subsequently randomized. In order to ensure transparent reporting of screen failure subjects, meet the Consolidated Standards of Reporting Trials (CONSORT) publishing requirements, and respond to queries from Regulatory authorities, a minimal set of screen failure information is required including Demography, Screen Failure details, Eligibility Criteria, and any Serious Adverse Events.

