#### **7.1.1. Time period for collecting AE and SAE information**

AEs will be collected from the start of study treatment and until the follow-up contact (as detailed in the SPM). Medical occurrences that begin prior to the start of study treatment but after obtaining informed consent may be recorded on the Medical History/Current Medical Conditions CRF.

SAEs will be collected over the same time period as stated above for AEs. However, any SAEs assessed as related to study participation (e.g., protocol-mandated procedures, invasive tests, or change in existing therapy) or related to a GSK product will be recorded from the time a subject consents to participate in the study up to and including any follow-up contact. All SAEs will be recorded and reported to GSK within 24 hours, as indicated in [Appendix 2](#).

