4. ANALYSIS POPULATIONS

Population	Definition / Criteria	Analyses Evaluated
Safety Population	Comprise of subjects who receive at least one dose of study medication.	Study Population Safety
Pharmacokinetic (PK) Population	Comprise of all randomised subjects of the Safety Population for whom a pharmacokinetic sample was obtained and analysed.	PK-Analyses
Pharmacodynamic (PD) Population	Comprise of all randomised subjects of the Safety Population for whom a pharmacodynamic measurement sample was obtained and analysed. Analysis will be based on the actual treatment the subject received for the assigned area	PD -Analyses
Per-Protocol Population	
 Comprise of all PD population subjects who receive at least one dose of study treatment and who comply with the protocol. Protocol deviations that would exclude subjects from the PP population are defined in Appendix 1 (Protocol Deviation Management Plan) for Definition Per-Protocol Population). 	As required for PD-Analyses

NOTES :

- Please refer to [Appendix 10](#): List of Data Displays which details the population to be used for each displays being generated.

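### SAP listings of screen failures, SAEs and randomised treatment are restricted to dosed subjects, so the first is empty and the other two omit anyone not dosed

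*SAP*

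**What the plan says.** **Who counts as a screen failure.** Protocol 4.4: "Screen failures are defined as subjects who consent to participate in the clinical trial but are never subsequently randomized". For these subjects, "a minimal set of screen failure information is required including Demography, Screen Failure details, Eligibility Criteria, and any Serious Adverse Events". The reasons given there are transparent reporting, CONSORT and regulatory queries.

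**When events are collected.** Protocol 7.1.1 starts general collection at dosing: "AEs will be collected from the start of study treatment and until the follow-up contact". SAEs on the same footing follow that window. SAEs related to study participation, such as those caused by protocol-mandated procedures, or related to a GSK product, are the exception: they "will be recorded from the time a subject consents to participate in the study up to and including any follow-up contact".

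**Who is in the SAP populations.** Safety, in SAP section 4: "Comprise of subjects who receive at least one dose of study medication". The PK population is "all randomised subjects of the Safety Population for whom a pharmacokinetic sample was obtained and analysed". The PD population is drawn from Safety in the same way, and Per-Protocol is drawn from PD. No screened, consented or randomised set is defined.

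**Which population each display uses.** SAP section 4 points to Appendix 10 for this. Appendix 10 puts Safety against listing 1 (randomised and actual treatment), listing 2 ("Listing of Reasons for Screen Failure"), listing 11 (exposure), listing 14 (SAEs), Table 1.1 (disposition) and Table 3.1 (exposure). The programming notes for listings 1, 2 and 14 are blank.

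**Randomised but not dosed.** SAP 11.4.2 assigns zero days of exposure to randomised subjects with no treatment start date.

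**The concern.** A listing of screen failures limited to dosed subjects cannot contain what its title promises. The same population label on listing 14 means that an SAE in someone who consented but was never dosed has no planned display, although the protocol has it recorded. The case is realistic. Protocol 6.4.1 applies four allergens plus positive and negative controls at screening, and protocol Table 6 names the hazard: "There have been rare reports of systemic allergic reactions following skin prick testing". Listing 1 would also omit any randomised subject who was not dosed, which are the rows for which randomised and actual treatment differ most.

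At stake is a complete account of subjects and of serious events in a first-in-human study. The size of a treatment effect is not at stake.

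**Working it through.** The plan gives no figure on this point and no arithmetic applies. The check is set logic on the definitions.

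1. **Listing 2.** Screen failure means consented and never randomised (Protocol 4.4). Safety means at least one dose (SAP section 4). Under the protocol, dosing follows randomisation. The overlap is therefore empty, and the listing has zero rows whatever the number of screen failures.

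2. **Possible exceptions to step 1.**
   - Re-screening in Parts B and C: protocol 4.4.1 gives the second attempt a new subject number. The failed attempt is undosed under its own number, and a subject later randomised is no longer a screen failure under 4.4.
   - A subject dosed in error without randomisation would fit the Safety wording and could enter listing 2. That would be a protocol violation, not planned content.
   - SAP 6.1 and 7.1.1 allow another population where one is specified. None is specified for these displays.

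3. **Listing 14.** For screen failures, protocol 4.4 asks for any SAE. For everyone, protocol 7.1.1 records participation-related SAEs from consent. A serious reaction to a screening skin prick falls under both. If the subject is later dosed, the population label does not exclude the event. If the subject is never dosed, it does. PK, PD and Per-Protocol all lie inside Safety, so no other planned display can hold the event.

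4. **Listing 1 and exposure.** Randomisation in Parts A and B is on Day -1 and dosing starts on Day 1 (SAP 2.3). In Part B a pregnancy test is due on Day 1 before dosing (Protocol 6.1.3). A subject excluded by that test is randomised but not dosed. She is not a screen failure under 4.4 and is in no SAP population. SAP 11.4.2 gives her zero days of exposure, but Table 3.1 and listing 11 are on Safety, so that rule can never produce a row.

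5. **Is this a version mismatch?** The SAP was written to protocol Amendment 2. The protocol's list of later changes adds 4.4.1 on re-screening and records no change to the 4.4 definition or to the 7.1.1 collection window. The conflict does not come from the SAP being out of date.

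**The case against.** **The intention is obvious.** Listing 2 is plainly meant to show screen failures, and a programmer might use all screened subjects regardless. That is a fair guess, but the SAP makes Appendix 10 the authority and defines no set for the programmer to use.

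**Protocol 4.4 requires information, not a SAP display.** This is correct. These SAEs are recorded, go to the sponsor within 24 hours (Protocol 7.1.1 and 7.1.7) and are subject to regulatory reporting (7.1.8). A reader might infer that a serious screening reaction would escape oversight. The documents do not support that; only the planned study output omits it.

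**The primary objective concerns the creams.** An SAE in someone who received neither cream says little about their safety. A reader might infer that the SAE summary (Table 3.5) is also on the wrong population, or that the primary endpoint is distorted. Neither follows. Table 3.5 on Safety is defensible, and the listing is the right place for events before dosing.

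**Few subjects are randomised and undosed.** This also stands. A reader might count anyone with a positive Day -1 drug screen among them. Protocol 3.1 and SAP 2.3 require eligibility before randomisation, and the SAP's Part B schedule (11.2.1.3) puts an eligibility review before randomisation on Day -1. Handled as planned, that subject is an ordinary screen failure. Part A enrols only women of non-childbearing potential, so the pregnancy-test example belongs to Part B. A probability for such a loss would need a rate that neither document gives.

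**Lost allocations would still be seen.** A reader might infer that a loss from the 3:1 allocation in Part B would be hidden. The SAP's tolerability and allergen-challenge shells print N by treatment, so a shortfall against plan would show. This SAP also still describes bilateral treatment of every subject, not a 3:1 parallel design.

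**Conclusion.** The point holds as a minor reporting fault. If the SAP is followed as written, listing 2 is empty, an SAE in a consented but undosed subject appears in no planned display, and randomised-but-undosed subjects are missing from listing 1 and from the exposure displays despite the rule in 11.4.2.

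The exclusion is complete by definition and needs no assumed rate. How many subjects it would touch cannot be derived from the documents. The conclusion assumes that Appendix 10 is applied literally and that nobody is dosed without being randomised. It does not extend to data collection, expedited safety reporting, dosing decisions, or any estimate or confidence interval.

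**What to change.** - In SAP section 4, add a set of all consented subjects and a set of all randomised subjects.
- In Appendix 10, assign listings 2 and 14 to all consented subjects. In listing 14, flag SAEs before first dose and SAEs in subjects never dosed; the latter have no treatment start date, so the onset derivation in SAP 11.4.3 returns missing for them.
- Assign listing 1 and Table 1.1 to the randomised set.
- Reconcile Table 3.1 and listing 11 with SAP 11.4.2: either show the zero-exposure subjects or remove the rule.
- Leave Table 3.5 and the other AE summary tables on Safety.

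The cost is two definitions, two population flags and a new label on a handful of displays. The protocol already has the data collected, and no protocol amendment is needed.
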